This study is a single-center, simple random parallel group design clinical trial, each random group is allocated according to the proportion of 1:1:1.

IV. Clinical trial site

Responsibilities: Second Affiliated Hospital of Zhejiang University; [name];
[contact];

Address: [name]
Province; [name]

Participation Unit: the Second Affiliated Hospital of Zhejiang University Medical College; person in charge: [name]

V. Design of research

1. Inclusion criteria

(1) Age 18-80 years old; (2) a teeth choice: 6-8 weeks after the teeth after the periodic treatment of teeth, there is at least one site periodontal diagnosis depth (PD) ≥ 5 mm, looseness is less than II The degree or II-III degree will be loose after a fixed fixed, imaging evaluation of the vertical bone absorption of the teeth is greater than 3 mm osteogenesis, and the site is free of teeth surgical treatment, the patient has no obvious symptoms; (3) Patients have better compliance, and the bacterial plaque control is good after the basic treatment (all-in-law bleeding index and the mushroom index), can understand the purpose of testing, willing to cooperate with surgery and follow-up, voluntarily participate in the test and signed Informed consent.

2. Exclusion criteria

(1) In the past 6 months, chewing smokeless tobacco, smoking or suction cigar once a week or more, or smoking more than 20 / week (1 pack / week); (2) patients before blood Three months taking any drug or platelet counts that affect platelet function less than 200,000 / mm³; (3) patients have taken anti-epileptic drugs, antiplasia, antidepressants, sedatives, califiers, anti-depression, sedatives in the

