A simple random method is used for random grouping. The specific method is as follows: first, a column number 1x 78 is established by Excel2013, and then the random number between 0 and 1 is generated by the other column, and then sorted by the largest to the smallest. The first 26 numbers are assigned to the GTR group, the middle 26 numbers are assigned to the APRF+GTR group, and the last 26 numbers are assigned to the CGF+GTR group. The subjects were divided into GTR group, APRF+GTR group and CGF+GTR group according to 1:1:1. (2) researcher A put the implant name (APRF or CGF or none) corresponding to the group mark into 78 Kraft paper envelopes with serial number 1: 78 and opaque according to the distribution order list. A gave the sealed envelope to B and no longer participated in the follow-up study. Researcher B is responsible for including the subjects according to the inclusion criteria, assigning the tested according to the order of seeing a doctor, and is responsible for supervising the operation process.

2. Blind design

Researcher A put the name of the implant corresponding to the group mark (APRF or CGF or none) into 78 Kraft paper envelopes with serial number 1x78 and opaque according to the assigned order list. A gave the sealed envelope to B and no longer participated in the follow-up study. Researcher B is responsible for including the subjects according to the inclusion criteria and assigning the number of the subjects according to the order of seeing a doctor. During the operation, researcher B will hand over the sealed envelope to the surgeon according to the number, supervise the operation process, and do not participate in other studies such as measurement. The survey researcher is responsible for measuring various indicators on a regular basis. Until the end of the experiment, the measurement researchers did not know how the subjects were grouped.

3. Treatment scheme

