(3) to compare the curative effect, first of all, the normality and homogeneity of variance of the experimental data were tested. If it obeys normality and homogeneity of variance, one-way analysis of variance (One-Way ANOVA) is used to compare the differences of mean among groups. If there were significant differences, pairwise comparisons were made, and multiple comparisons were made with SNK-q test to analyze and compare the differences between groups. If it does not obey normality and homogeneity of variance, Friedman test is used to compare the mean difference of each group; if there is significant difference, pairwise comparison is made by Wilcoxon Matched-Pairs Sighed Rank test. $P < 0.05$ was used as an index of statistical difference.

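### Minor free improvement: with exactly three arms and an F test already in place, plain pairwise t tests hold the same 5% family-wise level as SNK and are slightly more powerful

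*Combined protocol and SAP*

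**What the plan says.** Section III sets a parallel-group design in which "each random group is allocated according to the proportion of 1:1:1". Section VI.1 fixes the arms at 26: "The first 26 numbers are assigned to the GTR group, the middle 26 numbers are assigned to the APRF+GTR group", with the last 26 going to CGF+GTR, so 78 in all.

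Section VIII, item (3), describes the efficacy comparison: "If it obeys normality and homogeneity of variance, one-way analysis of variance (One-Way ANOVA) is used to compare the differences of mean among groups". It continues: "If there were significant differences, pairwise comparisons were made, and multiple comparisons were made with SNK-q test". The significance threshold is P < 0.05, with no sidedness stated.

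The pairwise step is therefore already conditional on a significant F test. The plan gives no reason for SNK, and does not say what will be reported if F is significant and SNK separates no pair. It states no effect size, SD, power or dropout rate.

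**The concern.** Section II sets out to compare three methods, so the pairwise results carry the answer. SNK applies a stricter critical value to the largest-versus-smallest difference and examines the other pairs only if that one passes. With four or more arms some such correction is needed, because a significant F does not protect the remaining true null hypotheses. With three arms the F test gives all the protection required.

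Two things are at stake, both modest: a little power, and the possibility of a significant F test with no pair named, for which the plan has no reporting rule.

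**Working it through.** **Inputs.** Three arms, 1:1:1 (Section III); 26 per arm (Section VI.1), so error df = 78 − 3 = 75; threshold 0.05, F test as gate (Section VIII). Effects and unequal arm sizes below are assumptions. The plan has no power figure to reproduce.

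**1. Error control without SNK.** Three means are either all equal, or at most one pair is equal.
- All equal: any false claim needs a significant F, which has probability 5%.
- One pair equal: only that pair can be falsely claimed, and its own t test has level 5%.

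So unadjusted t tests after a significant F (Fisher's protected LSD) have family-wise error of at most 5%. This is a closed test, and the bound is exact under the ANOVA assumptions.

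**2. Critical values at 75 df.**
- F(0.95; 2, 75) = 3.119.
- SNK, extreme pair: q(0.95; 3, 75)/√2 = 3.382/√2 = 2.391, an unadjusted p of about 0.019.
- SNK, adjacent pair: 1.992, the same as t(0.975; 75).

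Multiplying by √(2/26) = 0.277 gives a required extreme difference of 0.663 SD under SNK and 0.553 SD under the t test.

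**3. Significant F with no SNK pair.** At equal n, F = (t₁₂² + t₁₃² + t₂₃²)/3. If T is the largest |t| and the middle mean lies a fraction x of the way along, F = T²[1 + x² + (1 − x)²]/3. Hence T²/2 ≤ F ≤ 2T²/3. A significant F then forces T ≥ √(1.5 × 3.119) = 2.163. That is above 1.992, so protected t tests always name a pair. It can be below 2.391, so SNK may name none.

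**4. Error and power by simulation**, 26 per arm, at least 1,000,000 trials per scenario. Repeat runs differ by 0.1 to 0.2 points. Means are in SD units, in the order GTR and then the two concentrates.

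| Assumed means | SNK names a pair | Protected t names a pair |
|---|---|---|
| 0, 0.3, 0.3 | 16.6% | 17.8% |
| 0, 0.5, 0.5 | 40.9% | 43.0% |
| 0, 0.7, 0.7 | 70.7% | 72.8% |
| 0, 0.35, 0.7 | 57.5% | 59.3% |
| 0, 1, 1 | 95.7% | 96.4% |

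The largest loss found was about 2.3 points, at (0, 0.6, 0.6). A significant F with no SNK pair made up 4.9% of significant F tests at 0.5 SD and 2.0% at 0.8 SD. SNK never named a pair that the t tests missed.

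Family-wise error with all arms equal: 4.5% (SNK) and 5.0% (protected t). With two arms equal and the third far away: 5.0% for both.

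**5. Unequal arms**, assuming 26/24/21 analysed and SNK using the harmonic-mean size.
- GTR keeps 26: SNK 37.8% against 41.0% at 0.5 SD, and 66.7% against 70.2% at 0.7 SD, a loss of about 3 points. SNK's error for two truly equal concentrates reaches about 5.5 to 5.6%.
- GTR is the arm of 21: the loss is about 1.2 points and that error is about 4.4%.
- SNK now occasionally names a pair that the t tests do not, in up to about 1% of trials.
- A significant F still forces the largest |t| to at least 2.141, against 1.995 required at 68 df.

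**The case against.** The strongest reply is that the plan contains no error here. F-gated SNK is a valid procedure for three equal arms, and it contradicts nothing else in the documents. That stands, and it is why this is an improvement and not a fault. A reader might infer that SNK inflates the error rate; at the planned 26 per arm it does not.

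A reader might also infer that SNK buys nothing. That goes too far. Its guaranteed level is the same, but when all arms are equal it errs in 4.5% of trials and not 5.0%, and the added power comes from that unused alpha. With several outcomes and up to three visits each tested at 0.05, a little conservatism may look welcome. It was not designed for that purpose, though, and disappears when one arm is far from the other two.

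Three more limits hold. The result that SNK never names a pair the t tests miss applies to equal arms only. The pattern of two similar concentrates both beating GTR is an assumption: Section I suggests APRF may be the better of the two, while also reporting no significant difference in efficacy, so a graded pattern is shown as well. And a significant F with no SNK pair is uncommon (about 2% of all trials at 0.5 to 0.7 SD); a reporting sentence would deal with it. Protected t tests guarantee one named pair, not a full ranking of the methods.

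**Conclusion.** The point holds as a minor free improvement. For exactly three arms, with the F gate kept, the error guarantee of protected t tests follows from a proof and is not a matter of taste. At 26 per arm they lower the bar for the extreme pair from |t| 2.391 to 1.992 and always name a pair after a significant F.

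The gain is about 0.7 to 2.3 points of any-pair power over the assumed effects of 0.3 to 1.0 SD, and between about 1 and 3 points at 0.5 to 0.7 SD with arms of 26/24/21, depending on which arm is smallest. A claim of material power loss is not supported.

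The conclusion rests on normality and equal variance, and applies to one outcome at one visit. Mobility grade and bleeding on probing are unlikely to reach this branch. Multiplicity across outcomes and visits, and the non-normal branch, are separate matters.

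**What to change.** In Section VIII, item (3), replace the SNK-q test with:

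> Pairwise t tests using the ANOVA residual variance and actual group sizes, two-sided 5%, performed only if the overall F test is significant (Fisher's protected LSD, a closed test for three groups).

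Make the change before the data are analysed. It needs no more patients or measurements and keeps the 5% family-wise guarantee. The cost is one line of wording, plus the acknowledgement that the argument works because there are exactly three arms. If SNK is kept, add a sentence on how a significant F with no separated pair will be reported, and state how SNK will handle unequal group sizes.

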first 1 month before surgery Inflammatory drug or daily analgesic; (4) patients with diabetes history or blood glucose detection abnormal (fasting blood glucose $\geq 7\text{ mmol/L}$); (5) liver, renal function is abnormal (AST, Alt ≥ 1.5 times ULN, creatinine ≥ 1.5 times ULN); (6) has serious endocrine and metabolic diseases; (7) There are historical history of three high blood pressure; (8) History of osteoporosis; (9) History of autoimmune diseases; (10) Because of malignant tumors or other serious medical history, surgery should not be accepted or led to observation of teeth; (11) Pregnancy or lactating women; (12) Patients with anesthetic allergy; (13) Clinical or radiology shows that there are acute infections, root lesions, roots, severe eradications, dental bone rats, non-easy to abrasive, and osteoplasses (CEJ) or There is no treatment of untreated bilrels in the roots, the repair body is gains and / or in CEJ or the following repair edges are not in close; (14) A subject that can cause oral imaging inspection artifacts, such as: The study of teeth and its neighboring teeth are metal dentures, porcelain teeth; (15) a patient with root-stricken lesions;

3. Diagnostic criteria

(1) . Periodontal pocket $> 3\text{ mm}$, and inflammation, gingival bleeding (2) . Adjacent clinical attachment loss $> 1\text{ mm}$ (3) . Periodontal pocket bleeding on probing (4) . Alveolar bone has horizontal or vertical resorption. The progress of the disease is slow, and the teeth are loosened or displaced in the late stage.

4. Criteria for withdrawing / terminating tests

(1) . Any unexpected time to break blindness (2) . Patients who were found to be sensitive to or rejected implants during / after operation. (3) . Problems in need of treatment that met the exclusion criteria. (4) . Patients with irresistible factors such as non-migration / death lost follow-up during the study period.

VI. Research methods

1. Randomized controlled scheme

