CAL (clinical attachment level) : The distance from periodontal pocket bottom to CEJ was measured by periodontal probe (mm). Record six sites of each tooth (the mesial, median and distal site of the buccal and tongue surface).

mobility: use a tweezer to clamp the incisal areas of the anterior teeth or the pit groove on the occlusal surface of the posterior teeth and shake the teeth faciolingually, mesiodistally and vertically. I degree : abnormal mobility faciolingually or less than 1mm positioning. II degree : abnormal mobility faciolingually and mesiodistally or loosening range of 1-2mm. III degree : abnormal mobility faciolingually, mesiodistally and vertically or loosening range is

greater than 2mm.

BOP(bleeding of probe) : observe for 10-15 seconds after probe to see whether it bleeds. Record six sites of each tooth (the mesial, median and distal site of the buccal and tongue surface).

RBL(radiographic bone level): Locate the reference point at the deepest PD site of the affected tooth: cemento-enamel junction (CEJ), alveolar crest (AC), bone defect (BD) .RBL is the straight line distance from CEJ to BD (mm)

IC: IC is the straight line distance from AC to BD (mm)

regenerated bone volume parameters : in mimics software, threshold was set according to the gray value of the affected tooth and its surrounding alveolar bone, image editing and region growth were used to form a mask of the three-dimensional reconstruction area. The three-dimensional calculation function was used to reconstruct the three-dimensional shape of the alveolar bone in the target area. Furthermore, the structure of alveolar bone was optimized by remeshing and smooth. The volume of alveolar bone before and after operation was calculated by Boolean operation to obtain the model of regenerated alveolar bone and its volume was measured.

Defect fill (%) = (preoperative IC- and postoperative IC) / preoperative IC × 100%

Defect resolution (%) = (preoperative RBL- and postoperative RBL) / preoperative RBL × 100%

VIII. Statistical analysis method (statistical software: SPSS25.0)

1) data description: measurement data are described by mean \pm standard

deviation, non-normal distribution data are described by median and percentage (25th 75th percentile)

(2) baseline data are compared with normal distribution by one-way ANOVA test, while measurement data of non-normal distribution are described by Wilcoxon rank sum test.

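### The fallback efficacy tests (Friedman, Wilcoxon matched-pairs) are for related samples, but the three arms are independent, so the P value depends on file order and dropout discards observed patients

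*Combined protocol and SAP*

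**What the plan says.** Section III describes a "single-center, simple random parallel group design clinical trial" with 1:1:1 allocation. Section VI.1 builds the arms from one random sort of the numbers 1 to 78: "The first 26 numbers are assigned to the GTR group, the middle 26 numbers are assigned to the APRF+GTR group", and the last 26 go to CGF+GTR. No blocks, strata, matching, crossover or split-mouth element is described.

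Section VIII, item (3) first checks normality and equality of variance. If both hold, the arms are compared by one-way ANOVA with SNK-q pairwise tests. Otherwise: "If it does not obey normality and homogeneity of variance, Friedman test is used to compare the mean difference of each group". If that is significant, "pairwise comparison is made by Wilcoxon Matched-Pairs Sighed Rank test".

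For baseline data, item (2) uses an independent-sample test instead: "measurement data of non-normal distribution are described by Wilcoxon rank sum test".

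**The concern.** The Friedman test ranks the three conditions within each block, and the signed-rank test takes differences within each pair. Here no patient in one arm belongs with any particular patient in another. Software will still run both tests, treating the first row of each arm as one block, the second row as the next, and so on. Three things follow:

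- The P value depends on how the file happens to be sorted.
- Each arbitrary block compares only three patients, so information is lost.
- Once dropout makes the arms unequal, observed patients must be dropped to complete the rows. Section V.4 foresees patients "lost follow-up during the study period".

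The branch could well be used. Mobility is graded I to III. BOP is recorded by site as present or absent ("observe for 10-15 seconds after probe to see whether it bleeds"). Defect fill and defect resolution are ratios that may be skewed, and unequal variance is a second route in.

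**Working it through.** **Inputs from the documents.** Three parallel arms (section III); 26 per arm (section VI.1); significance level 0.05 (section VIII). The only figure that can be reproduced is 3 × 26 = 78, which agrees. No effect size, SD, power or dropout rate is given.

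**Assumptions.** GTR against two arms shifted equally by 0.5 to 0.9 SD; normal data, or log-normal data (sigma 0.5, additive shift); dropout of 5 to 20%, independent across arms.

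**Why row order enters.** With n = 26 rows and k = 3 arms, Friedman's statistic is Q = 12/[nk(k+1)] × ΣRj² − 3n(k+1), which here is (12/312) × ΣRj² − 312. Rj is the sum of ranks *within rows*, so a new row order changes Q. Kruskal-Wallis is H = 12/[N(N+1)] × Σ(Rj²/nj) − 3(N+1) with N = 78. It ranks all 78 values together and does not change with row order.

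**Row order** (30 simulated data sets per band, 2,000 orders each; median 2.5th and 97.5th percentiles of the Friedman P):

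| Data | Kruskal-Wallis P | Friedman P, 95% range | Orders with P < 0.05 |
|---|---|---|---|
| Continuous | 0.002–0.004 | 0.0005–0.10 | 89% |
| Continuous | 0.02–0.03 | 0.0035–0.34 | 47% |
| Continuous | 0.07–0.09 | 0.014–0.54 | 18% |
| Ordinal, four levels | 0.02–0.03 | 0.006–0.14 | 67% |
| Binary | 0.02–0.03 | 0.010–0.042 | 99% |

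Three separate log-normal data sets (log-SD 0.6, log-means 0/0.25/0.45) behaved alike. Kruskal-Wallis P was 0.032, 0.024 and 0.060, and 42%, 49% and 22% of orders gave a significant Friedman test. In the third set the signed-rank P for first against third arm ran from 0.0014 to 0.22, against a fixed Mann-Whitney P of 0.036.

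**Power, no dropout** (10,000 runs each, %):

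| Shift (SD) | 0.5 | 0.6 | 0.7 | 0.8 | 0.9 |
|---|---|---|---|---|---|
| Normal: Friedman | 31 | 42 | 56 | 68 | 79 |
| Normal: Kruskal-Wallis | 41 | 55 | 70 | 82 | 90 |
| Log-normal: Friedman | 47 | 62 | 74 | 83 | 91 |
| Log-normal: Kruskal-Wallis | 59 | 75 | 86 | 93 | 96 |

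From the unrounded values, the smallest loss is 96.4 − 90.7 = 5.7 points and the largest 69.7 − 55.7 = 14.0. Four ordinal scenarios lost 4 to 5 points (for example 59.5 against 54.4). A three-level one (40/45/15% against 75/20/5%) lost about 2. Four binary scenarios lost at most 1.

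For a single pair, signed-rank loses about 1 point to Mann-Whitney on normal data. On log-normal data it loses roughly 2 to 10, depending on how the shift is specified.

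**Dropout at rate d.** If rows are kept fixed, complete rows = 26(1−d)³, observed patients = 78(1−d), and discarded = 78(1−d) − 3 × 26(1−d)³. At 10%: 26 × 0.729 = 19.0 rows, and 70.2 − 56.9 = 13.3 discarded. If gaps are closed, the number of rows is the smallest arm.

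| Dropout | Discarded, fixed rows | Discarded, gaps closed | Friedman power at 0.8 SD, fixed / closed | Kruskal-Wallis power |
|---|---|---|---|---|
| 5% | 7.2 | 2.8 | 62 / 66% | 80% |
| 10% | 13.3 | 3.9 | 53 / 60% | 76% |
| 15% | 18.4 | 4.7 | 47 / 57% | 75% |
| 20% | 22.5 | 5.2 | 40 / 56% | 72% |

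**Type I error** of Friedman under an arbitrary order was 4.8% (normal), 4.8% (ordinal) and 5.5% (binary), so it is not inflated. Reporting the best of 5 orders gives 12.8%, and the best of 20 gives 25.6% (1,500 runs).

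**The case against.** The strongest reply is that the Friedman clause speaks of each group, outcomes are repeated over visits V0 to V3, and Friedman followed by signed-rank suits repeated visits within an arm. On that reading the row-order and cross-arm discarding problems vanish. It is the less natural reading, because the clause is the alternative to a between-arm ANOVA in a paragraph on comparing treatment effect. It would also leave the plan with no between-arm fallback, so item (3) needs rewriting either way.

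Second, the worst figures belong to continuous outcomes, for which use of the branch is not certain. For the outcomes most likely to reach it the harm is smaller: modest for ordinal mobility, close to nil for binary BOP. The plan also does not say that either is analysed under item (3), or how six BOP sites are coded. This stands and limits the expected size of the harm, but does not make the tests suitable.

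Third, nothing suggests that anyone would choose among row orders. That is fair. The best-of-several figures show only what an unspecified order permits, and the conclusion does not rest on them.

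Fourth, the larger discard counts need fixed rows, and the plan gives neither file layout nor dropout rate. Both layouts are therefore shown.

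**Conclusion.** The concern holds: the fallback branch of item (3) is wrong as written for this design and must be corrected before any between-arm analysis. The mismatch itself needs no assumption, because it follows from the design and the named tests.

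Its size does rest on assumed shifts, distributions and dropout. For continuous outcomes near the 0.05 boundary, file order alone can decide significance, and power falls by about 6 to 14 points before dropout. The loss is about 2 to 5 points for ordinal outcomes and 0 to 1 for binary ones. Dropout of 5 to 20% would discard roughly 3 to 23 observed patients, depending on rate and layout. No harm arises for outcomes that stay in the ANOVA branch. The rank sum wording in item (2), a two-sample test named for three groups, is a minor point.

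**What to change.** Rewrite the fallback in item (3):

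- **Non-normal data:** Kruskal-Wallis across the three arms, followed only if significant by pairwise Mann-Whitney or Dunn tests. If pairwise tests are to be run whatever the overall result, name a multiplicity adjustment.
- **Normal data with unequal variances:** Welch ANOVA with an unequal-variance pairwise procedure such as Games-Howell. Kruskal-Wallis does not cure unequal variances: with equal means and SDs of 1:1:3 it rejected in 6.5% of null simulations, against 4.9% for Welch.
- **Categorical outcomes:** analyse mobility as ordinal and state the BOP endpoint, for example bleeding at the defect site per patient, as binary with Fisher's exact test.
- **Visits:** if Friedman and signed-rank were meant for changes over time within an arm, say so and confine them to that use.

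In item (2), replace the rank sum test with Kruskal-Wallis.

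The cost is SAP wording plus one decision on whether BOP is analysed at the defect site, as a count or as a percentage. Conduct and data collection do not change.

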promote angiogenesis, inhibit osteoclasts, facilitate the migration and proliferation of gingival fibroblasts, and provide a good microenvironment for the repair and regeneration of traumatic tissue. On the other hand, in 2006, Sacco et al used inner wall coating test tube with silica, concentrated growth factor (CGF) was prepared after differential centrifugation. CGF uses differential centrifugation technology, so the fibrin clot obtained is larger than platelet-rich fibrin (PRF), and the content of fibrin is more. The three-dimensional fibrin network structure of CGF can be observed under scanning electron microscope, red blood cells and platelets are fixed in the fiber network, and the fiber of CGF is thicker and more regular than PRF. The contents and release rules of key growth factors in APRF/CGF were compared, and it was found that both APRF and CGF could stably release higher concentrations of growth factors PDGF- α β , TGF- β and VEGF, while APRF released more and more sustained growth factors than CGF in the later stage, suggesting that APRF may have better structure and function of promoting tissue repair and regeneration than CGF. However, there is no significant difference in the efficacy of APRF and CGF platelet concentrates in periodontal regeneration surgery, and there are some defects such as low level of evidence, small number of case samples, short observation period and so on. At present, there are still few studies on the application of the two in the treatment of clinical periodontal tissue regeneration, and there is no report on comparing the clinical effects of the two through randomized clinical controlled trials.

Based on this, this study compares the clinical application of GTR combined

with APRF/CGF and simple GTR in promoting periodontal bone defect regeneration through randomized clinical controlled trials, and intends to further explore the efficacy of the three methods in improving the amount of alveolar bone regeneration, so as to provide a certain basis for future clinical work.

II. The purpose of the clinical trial

The purpose of this study is to compare the clinical application of GTR combined with APRF/CGF and simple GTR in promoting periodontal bone defect regeneration, and to further explore the efficacy of the three methods in improving the amount of alveolar bone regeneration, so as to provide a basis for future clinical work.

III. Study design

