was completed, the symmetrical Medifuge centrifuge was selected, and the CGF procedure was selected and centrifuged for 13 minutes. The CGF centrifugation procedure is as follows: accelerate for 30 seconds, rise to 2700r/min, centrifuge for 2 minutes, then descend to 2400r/min, centrifuge for 4 minutes, accelerate to 2700r/min, centrifuge for 4 minutes, then descend to 3000r/min, centrifuge for 3 minutes, and decelerate to stop in the last 36 seconds. Finally, the blood in the test tube is divided into three layers: the top layer is PPP, the lowest layer is crimson jelly-like red blood cells and platelets, and the middle layer is yellow translucent gel-like CGF. The 2 test tubes completed by centrifugation were placed vertically on the operating compartment table for backup (not tilted or inverted). The APRF gel in the above process was changed to CGF gel, mixed and covered with CGF, and the other operations were the same.

If the patient was assigned to the GTR group, no blood was drawn. Gel or membrane containing growth factor was not used to cover the operation, and the rest of the operation was the same.

At the end of the operation, the surgeon gave the patient postoperative medical advice and given postoperative medication: cefuroxime axetil 50mg, ornidazole 500mg, twice a day for 5-7 days. Oral hygiene education was given to the patients again, and patients were advised to use Koutai mouthwash twice a day for 2 weeks, and about 2 weeks later to remove stitches. Two weeks after operation, stitches were removed by the original surgeon, and the patients were scheduled for 12 weeks \pm 7 days (V1), 24 weeks \pm 14 days (V2) and 48 weeks \pm 28

days (V3).

VII. Observation index and evaluation of curative effect

The patients were contacted and followed up by researcher B at 12, 24 and 48 weeks after operation. At 12 weeks \pm 7 days after operation, PD, CAL, mobility and BOP were measured by measurement researchers. 24 weeks \pm 14 days and 48 weeks \pm 28 days after operation, the researchers measured PD, CAL, mobility, BOP, RBL, IC, intraosseous defect angle and bone defect volume.

PD (probe depth) :use a periodontal probe (UNC-15,Hu-Friedy,Chicago,IL) paralleling to the long axis of the tooth to measure the distance from the bottom of the periodontal pocket to the gingival margin (mm), record six sites of each tooth (the mesial, median and distal site of the buccal and tongue surface).

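### No primary outcome or visit is named, and one P<0.05 rule covers 24 to 26 possible outcome-by-visit comparisons; if all are tested with no true difference, 1.2 to 1.3 false significant results are expected

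*Combined protocol and SAP*

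**What the plan says.** Section II gives the aim in general terms: "to further explore the efficacy of the three methods in improving the amount of alveolar bone regeneration". It names no measure and no time point.

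Section VII sets the schedule: "The patients were contacted and followed up by researcher B at 12, 24 and 48 weeks after operation". At 12 weeks, "PD, CAL, mobility and BOP were measured by measurement researchers". At 24 and 48 weeks, "the researchers measured PD, CAL, mobility, BOP, RBL, IC, intraosseous defect angle and bone defect volume". The same section defines two percentages from these measurements: "Defect fill (%) = (preoperative IC- and postoperative IC) / preoperative IC × 100" and "Defect resolution (%) = (preoperative RBL- and postoperative RBL) / preoperative RBL × 100". It also describes a regenerated volume, with pre- and post-operative bone "calculated by Boolean operation to obtain the model of regenerated alveolar bone and its volume was measured". Nothing here is ranked as primary or secondary, and no visit has priority.

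Section VIII, item (3), prescribes one-way ANOVA followed by SNK-q pairwise tests if the ANOVA is significant, or Friedman followed by Wilcoxon matched-pairs tests if the assumptions fail. It closes with one threshold: "P < 0.05$ was used as an index of statistical difference".

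**The concern.** The significance rule is attached to treatment effect in general, not to a named variable at a named visit. SNK-q handles the three arms within one outcome at one visit; nothing handles the many outcomes and visits. The main conclusion could therefore rest on whichever combination happens to cross 0.05.

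The stated purpose does not settle the choice. The amount of bone regeneration could mean regenerated volume, defect volume, defect fill or defect resolution, at week 24 or week 48, and these can disagree. Fill is computed from IC (alveolar crest to defect base) and resolution from RBL (cemento-enamel junction to defect base), so a change in crest height moves one and not the other. If the bone measures, the clinical measures or the two later visits point in different directions, the plan does not say which result answers the study question.

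**Working it through.** The documents give no power, effect size, SD or family-wise error figure, so there is no stated calculation to reproduce.

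**Count of three-arm comparisons** (Section VII, one summary value per tooth assumed)

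| Visit | Measured | Derived (fill, resolution) | Total |
|---|---|---|---|
| Week 12 | 4 | 0 | 4 |
| Week 24 | 8 | 2 | 10 |
| Week 48 | 8 | 2 | 10 |
| All | 20 | 4 | 24 |

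The documents do not say whether regenerated bone volume and bone defect volume are the same variable. If they differ, add one at each of weeks 24 and 48: 24 + 2 = 26.

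**Expected false significant results**, if all are tested and no arm differs on any outcome: m × 0.05.

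- m = 24: 24 × 0.05 = 1.2
- m = 26: 26 × 0.05 = 1.3

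Expectations add, so this needs no independence. The pairwise tests are gated on the overall test, so they do not add falsely significant outcomes in this setting.

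**Chance of at least one.** Under independence it is 1 − 0.95^m: 1 − 0.95^24 = 0.708 and 1 − 0.95^26 = 0.736. This is an implausible ceiling, because fill and resolution are computed from IC and RBL on the same tooth. Null simulations with 26 per arm, normal data, a one-way F test at 5% and an assumed common correlation (20,000 to 60,000 simulated trials per setting) give:

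| Assumed correlation | 24 tests | 26 tests |
|---|---|---|
| 0.3 | 60% | 63% |
| 0.5 | 47% | 49% |
| 0.7 | 33% | 34% |
| 0.8 | 25% | 26% |
| 0.9 | 17% | 17% |

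The mean number of false positives stays near 1.2 or 1.3 across these settings. The Friedman fallback is meant for matched data. Applied to arbitrarily paired independent arms, it had a simulated null size of about 0.047, so the expected count hardly changes if it is used.

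**What one primary test could detect** (one-way F, 5%, 80% power, noncentral F). For the largest difference d between arms in SD units, d = 3f/√2 if one arm differs from two equal arms, and d = f√6 if the arms are evenly spaced.

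- 26 per arm (Section VI.1), no losses: f = 0.359, so d = 0.76 or 0.88 SD
- 23 per arm (assumed, to show the effect of losses): f = 0.382, so d = 0.81 or 0.94 SD

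**The case against.** The strongest objection is to the count. Item (3) does not say that every variable is tested at every visit. It names tests of means and matched rank tests but no method for categorical data, so mobility grades and bleeding (six of the 24 cells) may fall outside it. Nor does it say that both IC and fill, or both RBL and resolution, are tested. Without the derived percentages 24 − 4 = 20 cells remain; without mobility and bleeding as well, 20 − 6 = 14. In the other direction, PD, CAL and bleeding are recorded at six sites per tooth with no stated summary, which could raise the number.

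This is fair, and it is why the figures are conditional on all 24 to 26 being tested. It does not remove the problem. At 14 cells the expected number is still 14 × 0.05 = 0.7, and the chance of at least one false positive is about 15% to 45% at correlations of 0.9 down to 0.3. Leaving the choice open until the data are seen is itself the fault.

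Two further points are partly right. The rule is not unrestricted in every respect, since pairwise tests follow only a significant overall test; it is unrestricted across outcomes and visits. And the aim is partly worded as exploration, so strict control over every outcome is not clearly required. But Section II also says the results should provide a basis for clinical work, and the plan neither labels itself exploratory nor names a main result.

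**Conclusion.** The concern holds. The documents name no primary outcome, primary visit, testing order or adjustment across outcomes and visits, and one 5% threshold applies to all treatment-effect comparisons.

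The firm figure is 1.2 to 1.3 expected false significant results over 24 to 26 tests. It assumes that all are tested, that each has size 0.05, that there is one summary per tooth, and that the arms do not truly differ. The chance of at least one is less certain, because the correlations are unknown. Even at an assumed 0.9 it is 17%, more than three times the nominal 5%.

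The missing decision rule matters as much as the error rate: several bone measures fit the purpose and none has priority. The change should be made; it is inexpensive and affects what the trial can conclude.

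**What to change.** Before unblinded data are examined, amend Sections VII and VIII as follows.

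- Name one primary outcome and one visit that match the stated purpose, for example CBCT regenerated bone volume at 48 weeks (V3).
- State whether regenerated bone volume and bone defect volume are the same variable.
- Test the overall arm effect on the primary outcome at 5%, and keep the existing rule that pairwise comparisons follow only a significant overall result.
- State the difference that 26 per arm can detect on that outcome.
- Label all other outcomes and visits secondary or exploratory and report estimates with 95% confidence intervals. If p-values are to support claims, adjust them; Holm's method is one option.

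The cost is protocol and SAP wording; the example primary uses CBCT images already planned. There are two downsides. A lone significant secondary result could no longer support an efficacy claim. And power for the chosen primary is unknown, because the documents give no effect size or SD: with 26 per arm and no losses, 80% power is reached only for a largest difference of about 0.76 to 0.88 SD, depending on how the arm means are spaced.
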